## **20 DATA COLLECTION**

Data that is not captured directly via an electronic device or instrument will be collected from source documents and entered into an eCRF within an electronic data capture (EDC) system. EDC security features will include the requirement for a unique user ID and password for each individual who make entries, reviews or makes changes to the data.

The investigator will be responsible for ensuring data is electronically captured or that it is entered into the eCRF in a timely manner relative to the subject visit. The investigator will

ensure the accuracy and completeness of all subject data specified in the protocol. Upon study completion, the data collected in the eCRF will be provided to each study site in portable document format (PDF).

## **21 REPORTING AND PUBLICATION**

All data generated in this study are the property of Asana BioSciences, LLC. An integrated clinical and statistical report will be prepared at the completion of the study. Publication of the results by the investigator will be subject to mutual agreement between the investigator and Asana BioSciences, LLC.

## **22 INVESTIGATOR OBLIGATIONS**

### **22.1 Regulatory Documents**

The investigator is responsible for creating and/or maintaining all study documentation required by 21 CFR 50, 54, 56 and 312, ICH E6 section 8, as well as any other documentation defined in the protocol or the Investigator Agreement. The investigator must maintain the documentation relating to this study and permit Asana BioSciences, LLC or a member of a regulatory agency access to such records.

The investigator must provide the following key documents to Asana BioSciences, LLC prior to the start of the study:

- A completed and signed Form FDA 1572. If during the course of the study any information reported on the Form FDA 1572 changes, a revised Form FDA 1572 must be completed and returned to Asana BioSciences, LLC for submission to the FDA. For studies executed outside the United States, documentation required by the governing regulatory authority may be substituted for the Form FDA 1572;
- A fully executed contract;
- The Investigator's Statement page in this protocol signed and dated by the investigator and any subsequent amendment signature pages;
- The IB acknowledgment of receipt page;
- Curricula vitae for the principal investigator and all sub-investigators listed on Form FDA 1572, including a copy of each physician's license (if applicable);
- A copy of the original IRB/IEC approval for conducting the study. If the study is ongoing, renewals must be submitted at yearly intervals or shorter intervals defined by the IRB/IEC. All subsequent modifications must be submitted and approved by the IRB, as described in section **19.1**;
- A copy of the IRB/IEC-approved informed consent form;
- A list of IRB/IEC members or DHHS Assurance Number;

- Laboratory certifications and normal ranges (if local labs are required by the protocol);
- Financial Disclosure Forms will be completed and signed by the investigator and all sub-investigators listed on Form FDA 1572. Investigator site staff that submitted an initial financial disclosure are also responsible for informing Asana BioSciences, LLC of any changes to their initial financial disclosure form throughout the duration of the study, and for up to 1 year after the completion of the study.

A complete list of required regulatory documents will be supplied by Asana BioSciences, LLC or its representative.

## **22.2 Delegation of Responsibilities and Adequate Resources**

The investigator should have adequate time to conduct the study properly and should have an adequate number of qualified staff to assist with the conduct of the study. The investigator shall delegate tasks only to individuals qualified by education, training and experience to perform the delegated tasks. The investigator or sub-investigator shall have direct oversight of or be easily accessible to all personnel with delegated activities. A log documenting delegation of responsibilities will be maintained throughout the study. The investigator is responsible for ensuring all delegated staff have been properly trained on the protocol and their assigned study responsibilities.

## **22.3 Medical Care of Study Subjects**

The investigator and/or a qualified sub-investigator shall be responsible for the subjects' medical care. Any unrelated medical condition discovered during the course of the study should be communicated to the subject so that they may seek appropriate medical care. The investigator will report all AEs as required by the protocol (section 12.5). The investigator will inform study subjects of new information regarding the study drug as it becomes available.

## **22.4 Use of Investigational Materials**

The investigator will acknowledge that the study drug supplies are investigational and as such must be used strictly in accordance with the protocol and only under the supervision of the principal investigator or sub-investigators listed on Form FDA 1572 (or other regulatory document, depending on region). Study drug must be stored in a safe and secure location. At study initiation, a representative from Asana BioSciences, LLC or designee will inventory the study drug at the site. The investigator must maintain adequate records documenting the receipt and disposition of all study supplies. The investigator is responsible for monitoring subject's use of the study drug to ensure compliance with the protocol. All unused ASN002 will be destroyed

at the investigational site, according to institutional standards after reconciliation by the clinical monitor. It is the investigator's responsibility to ensure that subjects return their medication.

## **22.5 Retention of Records**

Federal and local regulations require that the investigator retain a copy of all regulatory documents and records that support the data for this study (e.g., informed consents, laboratory reports, source documents, study drug dispensing records) for whichever of the following is the longest period of time:

- A period of 2 years following the final date of approval by the FDA or other regulatory agency of the study drug for the purposes that were the subject of the investigation; or
- A period of 5 years following the date on which the results of the investigation were submitted to the FDA or other regulatory agency in support of, or as part of, an application for a research or marketing permit for the study drug for the purposes that were the subject of the investigation.
- Longer retention times may be required by individual local, or national regulatory authorities. The investigator is responsible to understanding and complying with all retention requirements.

Asana BioSciences, LLC will notify investigators once one of the above 3 timeframes has been satisfied.

If the investigation does not result in the submission of the data in support of, or as part of, an application for a research or marketing permit, records must be retained according to applicable local and national governmental authority regulation.

If the investigator retires, relocates, or for other reasons withdraws from the responsibility of keeping the study records, custody must be transferred to a person who will accept the responsibility. Asana BioSciences, LLC must be notified in writing of the name and address of the new custodian. Study records should not be destroyed without consultation with Asana BioSciences, LLC.

## **22.6 Subject Confidentiality**

All subject records submitted to Asana BioSciences, LLC or its designee will be identified only by initials and code number. Subjects' names are not to be transmitted to Asana BioSciences, LLC. The investigator will keep a Master Subject List on which the ID number and the full name, address, and telephone number of each subject are listed. It is the investigators' responsibility to inform study subjects that representatives of the sponsor, FDA, or other

regulatory agencies may review all records that support their participation in the study. The investigator will adhere to all privacy laws to which he/she is subject.

## **22.7 Clinical Trials Registration**

The Sponsor will be responsible for entering information on the [www.ClinicalTrials.gov](http://www.ClinicalTrials.gov) website. Information on investigator name and site information may be disclosed as part of this posting.

## **23 TERMINATION OF STUDY**

The sponsor has the right to suspend or terminate the study at any time. The study may be suspended or terminated for any reason.

4	Completely disabled. Cannot carry on any selfcare. Totally confined to bed or chair
5	Dead

As published in Oken MM, Creech RH, Tormey DC, et al. Toxicity and response criteria of the Eastern Cooperative Oncology Group. *Am J Clin Oncol.* 1982; 5(6):649-655.

**Appendix C****PANEL OF PHARMACODYNAMIC MARKERS OF INFLAMMATION**

Human Inflammation MAP® v. 1.0					
#	Analyte	Short Name	#	Analyte	Short Name
1	Beta-2-Microglobulin	B2M	25	Tumor Necrosis Factor beta	TNF-beta
2	C-Reactive Protein	CRP	26	Brain-Derived Neurotrophic Factor	BDNF
3	Von Willebrand Factor	vWF	27	Eotaxin-1	
4	Alpha-2-Macroglobulin	A2Macro	28	Factor VII	
5	Ferritin	FRTN	29	Intercellular Adhesion Molecule 1	ICAM-1
6	T-Cell-Specific Protein RANTES	RANTES	30	Interleukin-1 alpha	IL-1 alpha
7	Tissue Inhibitor of Metalloproteinases 1	TIMP-1	31	Interleukin-1 beta	IL-1 beta
8	Tumor necrosis factor receptor 2	TNFR2	32	Interleukin-1 receptor antagonist	IL-1ra
9	Vascular Cell Adhesion Molecule-1	VCAM-1	33	Interleukin-12 Subunit p40	IL-12p40
10	Granulocyte-Macrophage Colony-Stimulating Factor	GM-CSF	34	Interleukin-12 Subunit p70	IL-12p70
11	Interferon gamma	IFN-gamma	35	Interleukin-15	IL-15
12	Interleukin-10	IL-10	36	Interleukin-17	IL-17
13	Interleukin-18	IL-18	37	Interleukin-23	IL-23
14	Interleukin-2	IL-2	38	Matrix Metalloproteinase-3	MMP-3
15	Interleukin-3	IL-3	39	Matrix Metalloproteinase-9	MMP-9
16	Interleukin-4	IL-4	40	Stem Cell Factor	SCF
17	Interleukin-5	IL-5	41	Vascular Endothelial Growth Factor	VEGF
18	Interleukin-6	IL-6	42	Alpha-1-Antitrypsin	AAT
19	Interleukin-7	IL-7	43	Fibrinogen	
20	Interleukin-8	IL-8	44	Haptoglobin	
21	Macrophage Inflammatory Protein-1 alpha	MIP-1 alpha	45	Vitamin D-Binding Protein	VDBP
22	Macrophage Inflammatory Protein-1 beta	MIP-1 beta			
23	Monocyte Chemotactic Protein 1	MCP-1			
24	Tumor Necrosis Factor alpha	TNF-alpha			

**Appendix D: DYNAMIC INTERNATIONAL PROGNOSTIC SCORING SYSTEM (DIPSS)**

Prognostic Variable	0 Points	1 Point	2 Points
Age (years)	$\leq 65$	$> 65$	
WBC ( $\times 10^9$ / L)	$\leq 25$	$> 25$	
Hemoglobin (g / dL)	$\geq 10$		$< 10$
Peripheral blood blasts	$< 1$	$\geq 1$	
Constitutional symptoms	No	Yes	

DIPSS score	DIPSS risk category
0	Low
1-2	Intermediate – 1
3-4	Intermediate – 2
5-6	High

## ABBREVIATIONS

$\alpha$	Significance level
AE	Adverse event
CR	Complete response
CRF	Case Report Form
CTCAE	Common Toxicity Criteria for Adverse Events
DLT	Dose-limiting toxicity
DOOR	Duration of Response
ECG	Electrocardiogram
ECOG	Eastern Cooperative Oncology Group
EP	Efficacy population
MedDRA	Medical Dictionary for Regulatory Activities
MRI	Magnetic resonance imaging
MTD	Maximum tolerated dose
NE	Non-evaluable
NR	No response
PD	Progressive disease or Pharmacodynamics
PFS	Progression-free Survival
PK	Pharmacokinetics
PP	Per-protocol
PR	Partial response or interval between the P wave and the QRS complex
q12H	Every 12 hours
QRS	Quasi-random signal
QT	QT interval
QTcB	QT interval, Bazett's formula
QTcF	QT interval, Frederica's formula
RECIST	Response Evaluation Criteria in Solid Tumors
RR	Interval between heart beats
SAE	Serious adverse event
SAF	Safety
SD	Stable Disease or Standard Deviation
SOC	System Organ Class
TEAE	Treatment-emergent adverse event
TTP	Time to Tumor Progression
WHO	World Health Organization

## DEFINITIONS OF TERMS

Part A	Part A, the dose escalation component of this study, will evaluate the safety and tolerability of ASN002 (study drug) including dose-limiting toxicities (DLT) and to determine the maximum tolerated dose (MTD).
Part B	Part B, the cohort expansion component of this study, will evaluate the safety, tolerability, and preliminary efficacy of ASN002 in subjects with relapsed/refractory diffuse large B-cell lymphoma (DLBCL), follicular lymphoma (FL), mantle cell lymphoma (MCL), peripheral T-cell lymphoma (PTCL), myelofibrosis (MF), and chronic lymphocytic leukemia (CLL).
Safety population	The safety population will include all subjects who take at least 1 dose of study medication. Safety analyses will be conducted using the safety population. The safety population will apply to Parts A and B.
Efficacy population	The efficacy population (EP) will include all subjects who have an evaluable screening and post-dose tumor assessment. The EP will be used as the supportive analysis population for efficacy endpoints.
PP population	The Per Protocol (PP) population will include all EP subjects without major protocol violations. The PP population will be used as the primary analysis population for efficacy.
Treatment Cohort	
There are nine treatment cohorts planned for Part A of this study:
 

Treatment Cohort 1 – 10 mg ASN002 q12H

Treatment Cohort 2 – 20 mg ASN002 q12H

Treatment Cohort 3 – 30 mg ASN002 q12H

Treatment Cohort 4 – 40 mg ASN002 q12H

Treatment Cohort 5 – 50 mg ASN002 q12H

Treatment Cohort 6 – 75 mg ASN002 q12H

Treatment Cohort 7 – 100 mg ASN002 q12H

Treatment Cohort 4a – 80 mg q24H

Treatment Cohort 5a – 120 mg q24H

Treatment-emergent	Symptoms or conditions with onset after the first administration of ASN002.

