---

**Investigational product, dosage and mode of administration:** ASN002 administered orally. Planned doses are 10, 20, 30, 40, 50, 75, and 100 mg q12h. Cohorts of subjects have been added to explore q24 h dosing, at 80 mg and 120 mg once daily. The initial qd dose will not exceed the total daily dose of the highest well tolerated bid dose. The initial dose taken with food will not exceed 75% of the highest tolerated dose. ASN002 is available in 5-mg, 20-mg, and 50-mg strength tablets.

**Duration of study:** Parts A and B will include a screening period (up to 28 days) and a treatment period up to 12 months. A subject with no DLTs may have the opportunity to continue treatment at the discretion of the investigator and sponsor. If the subject is not a candidate for, or chooses not to participate in additional treatment, an end-of-study visit will take place followed by a 4-week post-treatment period.

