#### 6.4.5 Rationale for the Evaluation of ASN002 with Food

Co-administration of ASN002 with a standardized low fat meal increased systemic exposure by about 80% in healthy subjects in a previous study. Future cohorts may evaluate safety and tolerability when ASN002 is administered immediately after a meal. The starting dose level at which the effect of a meal on safety, tolerability and pharmacokinetics will be evaluated will be

at least one dose lower than the highest dose evaluated when ASN002 was administered under fasted conditions

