## **8 INVESTIGATIONAL PLAN**

### **8.1 Study Design**

This study will be performed at approximately 3 to 15 study centers located in the United States and Latin America.

The study is an open-label, non-randomized, uncontrolled, multicenter, dose escalation, cohort expansion and extension study with single and multiple-dose PK in subjects with relapsed/refractory lymphomas, MF, CLL, and advanced/metastatic solid tumors for which no standard therapy exists. The study will be conducted in 2 parts:

- Part A: Evaluation of the safety and tolerability of escalating multiple doses of ASN002;
- Part B: Cohort expansion of 6 identified disease-specific cohorts (DLBCL, MCL, FL, PTCL, MF and CLL) from Part A to further evaluate the safety, tolerability and antitumor activity of multiple doses of ASN002.

Parts A will be a “3+3” dose escalation scheme beginning with dose level 1 at a dose of 10 mg every 12 hours. Subjects will receive a single dose of ASN002 on Day 1, followed by every 12 or 24 hours, as assigned, dosing beginning on Day 3. The dose of ASN002 will be escalated to identify DLTs, and the MTD. If an MTD is not identified by the last scheduled cohort, dose escalation will continue in less than or equal to 50% increments until the MTD is identified. If supported by the PK profile, transition to once daily dosing may be considered. The starting dose of the once daily (qd) dosing cohorts will not exceed the total daily dose of the highest twice daily dose that is considered safe and well tolerated. Daily dosing cohorts may include doses beginning at 60 mg QD. Additional dose escalation may be performed for the qd dose cohorts, if the MTD is not identified by the 100 mg qd dose.

[figure not shown]

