## 8.3 Selection of Doses

### 8.3.1 Part A (Dose Escalation)

Dose escalation will commence with dose level 1 (10 mg every 12 hours). Subsequent planned dose levels in Part A include: 20, 30, 40, 50, 75 and 100 mg administered every 12 hours or, 80, 120, and 150 mg every 24 hours. These planned dose levels may be modified based on data obtained throughout the course of study conduct. If an MTD is not identified after completion of the highest scheduled dosing cohort (either bid or qd) dose escalation may continue in

increments of  $\leq 50\%$  until the MTD is identified. The doses for twice daily and the single daily doses are found in **Table 6**.

The PK of ASN002 may be evaluated when administered with food. Up to 6 subjects per dose cohort may receive ASN002 after consuming a light meal. Subjects receiving ASN002 with food will receive no more than 75% of the highest dose that is deemed safe and well tolerated.

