**Table 6: Twice Daily and Once Daily Dosing Cohorts**

Twice Daily Dose Cohorts		Single Daily Dose Cohorts	
1	10 mg	N/A	
2	20 mg	N/A	
3	30 mg	N/A	
4	40 mg	4a a	80 mg
5 a	50 mg	5a a	120 mg
6 a	75 mg	6a a	150 mg
7 a	100 mg		

a Cohorts may be administered ASN002 with and/or without food.  
Dose escalation may continue in increments of  $\leq 50\%$  until the MTD is identified

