## 4 SAMPLE SIZE CONSIDERATIONS

### Part A:

A traditional 3+3 design will be used to identify the MTD. In addition to the 40 subjects enrolled in the previous amendments, an additional 24 subjects may be enrolled and dose in either fed or fasted states. A total of 64 subjects will be enrolled into the Part A dose escalation phase of the study. No randomization will be performed for Part A.

Part B: A sample size of 84 subjects (14 each in DLBCL, MCL, FL, PTCL, MF, and CLL) will be enrolled. The null hypothesis that the true response rate is 0.05 will be tested against a one-sided alternative. A total of 14 patients will be accrued in each cohort. The null hypothesis will be rejected if at least 3 responses are observed in 14 subjects. This design yields a type I error rate of 0.02 and power of 0.9 when the true response rate is 0.4.

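### The SAP's Part A treatment cohorts carry no food state, so any fed subjects would share a table column with fasted subjects at the same dose

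*SAP*

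**What the plan says.** **Cohort definition.** SAP Definitions of Terms: "There are nine treatment cohorts planned for Part A of this study". The list is 10, 20, 30, 40, 50, 75 and 100 mg q12H, and 80 and 120 mg q24H. Food state is not part of any label.

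**Fed dosing.** Protocol Table 6 marks cohorts 4a, 5, 5a, 6, 6a and 7 with the footnote "Cohorts may be administered ASN002 with and/or without food", so fed and fasted subjects share a cohort number. Section 8.3.1 allows up to 6 fed subjects per dose cohort, and Section 15.1 anticipates up to 4 fed cohorts. SAP Section 4 says that "an additional 24 subjects may be enrolled and dose in either fed or fasted states", on top of 40 already enrolled. The protocol's amendment rationale gives evaluation of safety and tolerability with a meal as a reason for amending Part A.

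**Food effect and dose limit.** Protocol 6.4.5: "Co-administration of ASN002 with a standardized low fat meal increased systemic exposure by about 80% in healthy subjects in a previous study". Protocol 8.3.1: "Subjects receiving ASN002 with food will receive no more than 75% of the highest dose that is deemed safe and well tolerated".

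**Reporting unit.** TEAEs (SAP 10.1), exposure (10.2), laboratory values (10.4) and biomarkers (9.5.1) are summarised by treatment cohort, and QTcF percentages (10.7) use the treatment cohort as denominator. SAP 6.2 and 6.3 plan no strata, covariates or subgroups.

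**Once-daily levels.** Protocol 8.3.1 has "80, 120, and 150 mg every 24 hours" and Table 6 agrees. The synopsis has "Cohorts of subjects have been added to explore q24 h dosing, at 80 mg and 120 mg once daily". Section 8.1 has "Daily dosing cohorts may include doses beginning at 60 mg QD" and also refers to a 100 mg once-daily level.

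**The concern.** A subject given 75 mg q12H after a meal has only one place to go under the SAP: Treatment Cohort 6, beside subjects given 75 mg q12H fasted. If food raises exposure as much as the protocol reports, that column mixes two quite different exposures under one dose label.

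Two things are at stake. First, Part A was amended partly to learn whether the drug is tolerated with food, and safety is analysed in this SAP (pharmacokinetics has its own plan). No summary in it would answer that question. Second, the dose-toxicity pattern across columns becomes harder to read. This matters most at 75 mg BID, the Part B dose, which Protocol 8.4 has taken on an empty stomach outside the food cohorts.

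Protocol Section 15 gives the SAP priority where the two documents differ, and SAP Section 14 declares no changes from the protocol. The SAP definition would therefore govern as it stands.

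**Working it through.** **1. Part A size.** Inputs: 40 enrolled and 24 additional (SAP 4); up to 4 fed cohorts (Protocol 15.1) of up to 6 (Protocol 8.3.1). 40 + 4 × 6 = 64, which reproduces the stated total. Ceiling on the fed share: 24/64 = 37.5%. It is a ceiling because the extra subjects may be dosed fed or fasted.

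**2. Cohort lists compared.** The SAP has 9 dose-by-schedule cohorts and Protocol Table 6 has 10; the difference is 6a (150 mg once daily). Table 6 marks 6 cohorts for possible fed dosing, of which 5 are in the SAP list: 50, 75 and 100 mg BID, and 80 and 120 mg once daily. None is split by food in either document.

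**3. Would a fed cohort meet fasted subjects at the same dose?** The amendment rationale says dosing so far has been fasted, and Protocol 6.4.2 cites data from cohorts 1 to 6 and 4a. A fed cohort opened at 50 or 75 mg BID would therefore join a column that already holds fasted subjects.

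**4. Size of the exposure difference.** Ratio = 1 + 0.80 = 1.8. Assumptions not established in the documents: exposure is proportional to dose, and the healthy-subject effect of a low-fat meal carries over to patients taking a light meal.

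- 50 mg BID fed: 50 × 1.8 = 90 mg BID fasted-equivalent, above the 75 mg fasted level.
- 75 mg BID fed: 75 × 1.8 = 135 mg, above the 100 mg fasted level. Under the limit in 8.3.1 this dose is open only if 100 mg BID is deemed safe and well tolerated (0.75 × 100 = 75). If 75 mg is the highest such dose, the limit is 0.75 × 75 = 56.25 mg. Protocol 6.4.2 instead ties the 75% to the highest dose administered fasted, so the condition depends on which passage is read.
- At the limit itself: 0.75 × 1.8 = 1.35 times the exposure of the highest tolerated fasted dose.

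Range: under proportionality, 50 mg fed exceeds 75 mg fasted when the food ratio is above 75/50 = 1.5, and 75 mg fed exceeds 100 mg fasted when it is above 100/75 = 1.33. The ordering would survive a food effect somewhat smaller than 1.8.

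**5. What a pooled column would show.** Mean exposure relative to fasted:

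| Fasted : fed | Calculation | Ratio |
|---|---|---|
| 6 : 3 | (6 + 3 × 1.8)/9 | 1.27 |
| 6 : 6 | (6 + 6 × 1.8)/12 | 1.40 |
| 3 : 6 | (3 + 6 × 1.8)/9 | 1.53 |

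Illustration: an adverse event in 0/6 fasted and 2/6 fed subjects (33.3%) would print as 2/12 (16.7%).

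**The case against.** The strongest reply is that the SAP nowhere says it will pool. That is true: pooling is inferred from a cohort definition without food state, tables built on that definition, and no strata or subgroups. Fed dosing is also optional throughout both documents, so the problem may never arise. Both points stand and make the conclusion conditional. They do not remove it, because the SAP supplies no other rule for placing a fed subject.

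Second, the gap begins in the protocol, which gives fed and fasted subjects one cohort number and summarises by dose level. That also stands; the SAP inherits the gap rather than creating it.

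Third, a reader might infer that escalation or the MTD is compromised. The documents do not support that. The safety review committee decides cohort by cohort on the latest data (Protocol 8.5.1, SAP 11.1), and DLTs are listed by subject. Individual subjects also remain visible in the listings. The effect is confined to descriptive tables and how they are read.

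Fourth, a reader might link the absence of 150 mg once daily to the food problem, or think that SAP Section 4 plans that dose. Neither holds. Leaving out that level pools no fed with fasted subjects, and SAP Section 4 mentions food state only. The SAP's once-daily levels match the synopsis, so this is a separate inconsistency.

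Finally, splitting every table could yield many small columns. That is a fair limit on the remedy.

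**Conclusion.** The point holds in conditional form. If fed subjects are enrolled at a dose that also has fasted subjects, the SAP as written would place both in the same column of the TEAE, exposure, laboratory, QTcF and biomarker tables. At most 24 of 64 Part A subjects (37.5%) could be fed. On the protocol's 1.8-fold figure, with dose proportionality and the same effect in patients assumed, a 50 mg BID fed group would sit above the 75 mg BID fasted level. The 135 mg equivalent for 75 mg BID fed needs the further condition on 100 mg BID described above and should not be quoted without it.

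The consequence is a misleading safety-by-dose summary and no tabulated answer to the food-tolerability question. It should be corrected before the tables are programmed. The disagreement over once-daily levels is a separate matter: subjects at a level missing from the SAP list would have no defined cohort and no expected total dose under SAP 7.3.

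**What to change.** In the SAP, define treatment cohort as dose by schedule by food state. Wherever fed subjects are enrolled, show fed and fasted in separate columns, at least in the TEAE, exposure, laboratory, QTcF and biomarker tables. Add food state to the DLT listing and record the change in SAP Section 14.

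Separately, reconcile the once-daily levels in the protocol synopsis, Section 8.1, Section 8.3.1 with Table 6, and the SAP definition. The SAP cohort list and the expected-dose derivation in SAP 7.3 should then follow the reconciled list. Which levels belong there is for the sponsor to settle.

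The cost is one definition and some extra columns. On the present Table 6 the maximum is 10 + 6 = 16 groups; with the up to 4 fed cohorts anticipated it is 10 + 4 = 14. Some columns will hold few subjects, which is already usual in a 3+3 design. Tables without fed subjects need no change.
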